11.1.4 Response Criteria

11.1.4.1 Evaluation of Target Lesions

Complete Response (CR): Disappearance of all target lesions. Any pathological lymph nodes (whether target or non-target) must have reduction in short axis to <10 mm.

Partial Response (PR): At least a 30% decrease in the sum of the diameters of target lesions, taking as reference the baseline sum diameters.

Progressive Disease (PD): At least a 20% increase in the sum of the diameters of target lesions, taking as reference the smallest sum on study (this includes the baseline sum if that is the smallest on study). In addition to the relative increase of

20%, the sum must also demonstrate an absolute increase of at least 5 mm. (Note: the appearance of one or more new lesions is also considered progressions).

Stable Disease (SD): Neither sufficient shrinkage to qualify for PR nor sufficient increase to qualify for PD, taking as reference the smallest sum diameters while on study.

11.1.4.2 Evaluation of Non-Target Lesions

Complete Response (CR): Disappearance of all non-target lesions and normalization of tumor marker level. All lymph nodes must be non-pathological in size (<10 mm short axis).

Note: If tumor markers are initially above the upper normal limit, they must normalize for a patient to be considered in complete clinical response.

Non-CR/Non-PD: Persistence of one or more non-target lesion(s) and/or maintenance of tumor marker level above the normal limits.

Progressive Disease (PD): Appearance of one or more new lesions and/or *unequivocal progression* of existing non-target lesions. *Unequivocal progression* should not normally trump target lesion status. It must be representative of overall disease status change, not a single lesion increase.

Although a clear progression of “non-target” lesions only is exceptional, the opinion of the treating physician should prevail in such circumstances, and the progression status should be confirmed at a later time by the review panel (or Principal Investigator).

11.1.4.3 Evaluation of New Lesions

The finding of a new lesion should be unequivocal (i.e. not due to difference in scanning technique, imaging modality, or findings thought to represent something other than tumor (for example, some ‘new’ bone lesions may be simply healing or flare of pre-existing lesions). However, a lesion identified on a follow-up scan in an anatomical location that was not scanned at baseline is considered new and will indicate PD. If a new lesion is equivocal (because of small size etc.), follow-up evaluation will clarify if it truly represents new disease and if PD is confirmed, progression should be declared using the date of the initial scan on which the lesion was discovered.

11.1.4.4 Evaluation of Best Overall Response

The best overall response is the best response recorded from the start of the treatment until disease progression/recurrence (taking as reference for progressive disease the smallest measurements recorded since the treatment started). The patient's best

response assignment will depend on the achievement of both measurement and confirmation criteria.

For Participants with Measurable Disease (i.e., Target Disease)

Target Lesions	Non-Target Lesions	New Lesions	Overall Response	Best Overall Response when Confirmation is Required*
CR	CR	No	CR	≥4 wks Confirmation**
CR	Non-CR/Non-PD	No	PR	≥4 wks Confirmation**
CR	Not evaluated	No	PR	
PR	Non-CR/Non-PD/not evaluated	No	PR	
SD	Non-CR/Non-PD/not evaluated	No	SD	Documented at least once ≥4 wks from baseline**
PD	Any	Yes or No	PD	no prior SD, PR or CR
Any	PD***	Yes or No	PD	
Any	Any	Yes	PD	

* See RECIST 1.1 manuscript for further details on what is evidence of a new lesion. ** Only for non-randomized trials with response as primary endpoint. *** In exceptional circumstances, unequivocal progression in non-target lesions may be accepted as disease progression.
 
Note: Participants with a global deterioration of health status requiring discontinuation of treatment without objective evidence of disease progression at that time should be reported as “symptomatic deterioration.” Every effort should be made to document the objective progression even after discontinuation of treatment.
				

For Participants with Non-Measurable Disease (i.e., Non-Target Disease)

Non-Target Lesions	New Lesions	Overall Response
CR	No	CR
Non-CR/non-PD	No	Non-CR/non-PD*
Not all evaluated	No	not evaluated
Unequivocal PD	Yes or No	PD
Any	Yes	PD

* ‘Non-CR/non-PD’ is preferred over ‘stable disease’ for non-target disease since SD is increasingly used as an endpoint for assessment of efficacy in some trials so to assign this category when no lesions can be measured is not advised
		

11.1.5 Duration of Response

Duration of overall response: The duration of overall response is measured from the time measurement criteria are met for CR or PR (whichever is first recorded) until the first date that recurrent or progressive disease is objectively documented (taking as reference for progressive disease the smallest measurements recorded since the treatment started, or death due to any cause. Participants without events reported are censored at the last disease evaluation).

Duration of overall complete response: The duration of overall CR is measured from the time measurement criteria are first met for CR until the first date that progressive disease is objectively documented, or death due to any cause. Participants without events reported are censored at the last disease evaluation.

Duration of stable disease: Stable disease is measured from the start of the treatment until the criteria for progression are met, taking as reference the smallest measurements recorded since the treatment started, including the baseline measurements.

11.1.6 Progression-Free Survival

Overall Survival: Overall Survival (OS) is defined as the time from first treatment to death due to any cause, or censored at date last known alive.

Progression-Free Survival: Progression-Free Survival (PFS) is defined as the time from first treatment to the earlier of progression or death due to any cause. Participants alive without disease progression are censored at date of last disease evaluation.

Time to Progression: Time to Progression (TTP) is defined as the time from first treatment to progression, or censored at date of last disease evaluation for those without progression reported.

DATA REPORTING / REGULATORY REQUIREMENTS

Adverse event lists, guidelines, and instructions for AE reporting can be found in Section 7.0 (Adverse Events: List and Reporting Requirements).

12.1 Data Reporting

12.1.1 Method

The Office of Data Quality (ODQ) will collect, manage, and perform quality checks on the data for this study.

12.1.2 Responsibility for Data Submission

Investigative sites within DF/HCC or DF/PCC are responsible for submitting data and/or

data forms to the Office of Data Quality in accordance with DF/HCC SOPs.

12.2 Data Safety Monitoring

The DF/HCC Data and Safety Monitoring Committee (DSMC) will review and monitor toxicity and accrual data from this study. The committee is composed of clinical specialists with experience in oncology and who have no direct relationship with the study. Information that raises any questions about participant safety will be addressed with the Overall PI and study team.

The DSMC will review each protocol up to four times a year or more often if required to review toxicity and accrual data. Information to be provided to the committee may include: up-to-date participant accrual; current dose level information; DLT information; all grade 2 or higher unexpected adverse events that have been reported; summary of all deaths occurring with 30 days of intervention for Phase I or II protocols; for gene therapy protocols, summary of all deaths while being treated and during active follow-up; any response information; audit results, and a summary provided by the study team. Other information (e.g. scans, laboratory values) will be provided upon request.

STATISTICAL CONSIDERATIONS

13.1 Study Design/Endpoints

I. Primary Objectives

- a. To evaluate the overall response rate in uveal melanoma to ERK inhibitor therapy.

II. Secondary Objectives

- a. To characterize the safety profile of ERK inhibitor therapy when administered to adult patients with unresectable or metastatic uveal melanoma
- b. To evaluate overall survival of patients with uveal melanoma treated with ERK inhibitor therapy.
- c. To evaluate the pharmacodynamics of ERK inhibition with a comparison of pre- and on-treatment biopsies.

13.2 Sample Size, Accrual Rate and Study Duration

We would consider ERK inhibition therapy effective in the treatment of uveal melanoma if a 25% response rate was observed. To assess this, we will conduct a two-stage design comparing a null rate of 5% against the alternative rate of 25%. Thirteen patients will be enrolled into the first stage of the trial and if one or fewer responses are observed the trial will be terminated for lack of efficacy. If two or more responses are seen, an additional 12 patients will be enrolled into the second stage of the trial. If a total of three or more of the 25 total patients

have a response the treatment would be considered promising. With this number of patients there is a 1 sided type-1 error of 8% (target 10%) and 87% power (target 85%). If the true response rate is 5% then the probability is 0.86 of stopping at the end of the first stage.

Uveal melanoma, similar to cutaneous melanoma, is a disease which is predominantly found in patients of Caucasian descent. Thus our study will not have many patients from racial categories other than White with a few patients who are Hispanic or Latino.

Accrual Targets				
Ethnic Category	Sex/Gender			
	Females		Males	Total
Hispanic or Latino	2	+	3	= 5
Not Hispanic or Latino	8	+	12	= 20
Ethnic Category: Total of all subjects	10	+	15	= 25
Racial Category				
American Indian or Alaskan Native		+		=
Asian		+		=
Black or African American		+		=
Native Hawaiian or other Pacific Islander		+		=
White	10	+	15	=
Racial Category: Total of all subjects	10	+	15	= 25

(A1 = A2) (B1 = B2) (C1 = C2)

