13.5 Analysis of Primary Endpoints

The primary endpoint for this study is overall response rate in uveal melanoma by standard solid

tumor response criteria. The proportion of patients with best response of CR or PR will be presented with a 90% confidence interval estimated using the method of Atkinson and Brown, which allows for the two stage design.

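### Does Section 13.2 set two conflicting success criteria (3 of 25 against an observed 25%), and does the 90% interval contradict the decision rule?

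*Combined protocol and SAP*

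**What the plan says.** Section 13.2 begins: "We would consider ERK inhibition therapy effective in the treatment of uveal melanoma if a 25% response rate was observed". The following sentence sets up a two-stage design, "comparing a null rate of 5% against the alternative rate of 25" per cent. With 13 patients in stage 1, "if one or fewer responses are observed the trial will be terminated for lack of efficacy". Otherwise, "If two or more responses are seen, an additional 12 patients will be enrolled into the second stage of the trial". The final rule is "If a total of three or more of the 25 total patients" "have a response the treatment would be considered promising". For this design the section states a one-sided type I error of 8% against a 10% target, power of 87% against an 85% target, and a 0.86 chance of stopping at stage 1 if the true rate is 5%.

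Section 13.5 says that the proportion with a best response of CR or PR "will be presented with a 90% confidence interval estimated using the method of Atkinson and Brown", a method chosen because it allows for the two stages. It does not make exclusion of 5% a condition of success. Section 13.6 uses the same 90% level for the disease control rate and the time-to-event estimates.

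**The concern.** Read literally, the opening sentence of 13.2 attaches the label effective to an observed 25%. With 25 patients that means at least 7 responses, since 6/25 is 24%. The decision rule attaches the label promising to 3/25. The section does not say how the two labels differ, and the stated error and power belong only to the second.

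There is also a difference in levels. The test is one-sided with a 10% target, whereas a two-sided 90% interval leaves 5% in each tail. If the test's actual error lies above 5%, the interval at the boundary count must include the null. A report of 3/25 would then call the drug promising beside an interval that does not rule out a 5% response rate. If all three readings were live criteria, the primary conclusion could be chosen after the data were seen.

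**Working it through.** **Inputs.** From 13.2: null rate 5%, alternative 25%, n1 = 13, stop if 1 or fewer responses, 12 further patients, promising if 3 or more of 25. From 13.5: 90% two-stage interval. From 2.3: the 14% response rate reported for selumetinib, used here only as an intermediate true rate.

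**Step 1: reproduce the stated figures.** Let X1 be the stage 1 count.

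- P(stop) = (1−p)^13 + 13p(1−p)^12.
- The only continuing path that fails is 2 responses in stage 1 and 0 in stage 2. So P(promising) = 1 − P(stop) − P(X1 = 2)(1−p)^12.

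At p = 5%:
- P(stop) = 0.5133 + 0.3512 = 0.8646.
- P(promising) = 1 − 0.8646 − 0.1109 × 0.5404 = 0.1354 − 0.0599 = 0.0755.

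At p = 25%:
- P(stop) = 0.0238 + 0.1029 = 0.1267.
- P(promising) = 1 − 0.1267 − 0.2059 × 0.0317 = 0.8733 − 0.0065 = 0.8668.

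Rounded, these are the plan's 0.86, 8% and 87%.

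**Step 2: the literal reading of observed.** Requiring stage 1 to be passed and at least 7/25 gives a type I error of 0.00016 and power of 0.433. Accepting 6/25 as close enough gives 0.0011 and 0.604. Neither pair resembles the stated 8% and 87%, so the figures in 13.2 cannot have been derived for an observed-25% rule.

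**Step 3: the interval at the boundary.** The outcomes rank 0/13, 1/13, 2/25, 3/25 and so on, whether by stage and then count or by observed proportion (0, 7.7%, 8%, 12%).

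- The lower 90% limit at 3/25 solves P(promising | p) = 0.05, giving p = 0.0420.
- The upper limit solves 1 − P(continue and total ≥ 4 | p) = 0.05, giving p = 0.3276.
- The one-sided p-value at 5% is 0.0755. It exceeds 0.05, so the lower limit must fall below 5%.

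| Result | 90% two-stage interval | 80% two-stage interval | One-sided p at 5% |
|---|---|---|---|
| 3/25 | 4.2% to 32.8% | 5.7% to 28.5% | 0.0755 |
| 4/25 | 6.2% to 35.1% | 7.8% to 31.1% | 0.0261 |
| 5/25 | 8.5% to 38.4% | 10.4% to 34.7% | 0.0063 |

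The 90% interval includes 5% at 3/25 and at no higher count.

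**Step 4: how often 3/25 occurs.** P(exactly 3/25) = P(promising) − P(continue and total ≥ 4).

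- True 5%: 0.0755 − 0.0261 = 0.0494.
- True 14%: 0.121, out of a 0.514 chance of a promising result.
- True 25%: 0.8668 − 0.8327 = 0.0341.

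As shares of promising results these are 65%, 24% and 4%. The 65% is a share of an event that itself has probability 7.5%.

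**The case for a change.** The strongest case for a change is that the protocol does say observed, and that the affected region is not rare. Counts of 3 to 6 of 25 are promising yet below an observed 25%. They make up 50% of promising results at a true 25%, since (0.8668 − 0.4330)/0.8668 = 0.50, and 90% at a true 14%. The interval is also the only inferential summary planned for the primary endpoint, and nothing warns that it may sit awkwardly beside the decision. An 80% interval would put 10% in each tail, match the test's target and exclude 5% at 3/25. The change would be wording only.

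Part of this stands. The word is wrong for a design parameter, and a reader who took the opening sentence alone would be misled. But the shares for 3 to 6 of 25 matter only if an observed 25% is a criterion. The sentence that follows presents the two-stage design as the way to assess the claim, with 25% as the alternative rate, and no threshold other than 3/25 is given.

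On the interval, an 80% level is a defensible preference, not a correction. The 90% interval is a valid estimate. It agrees with the 90% level used in 13.6, and it shows the uncertainty in a 25-patient estimate more cautiously. A test with a 7.5% tail and an interval with 5% tails can both be reported without contradiction.

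**Conclusion.** The concern does not call for a change. The opening sentence of 13.2 contains a slip: 25% is the true rate that the design is powered to detect, not an observed rate to be reached. One prespecified rule governs the conclusion, and its operating characteristics are correct as stated. An analyst following the plan would apply the rule of at least 3/25 and reach a sound conclusion. Correcting the word would alter no decision, error rate or result.

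The difference between test level and interval level is real but narrow. It appears only at exactly 3/25, with probability 4.9%, 12.1% and 3.4% at true rates of 5%, 14% and 25%. There the report can simply state that the count met the rule with a one-sided p of 0.0755 and that the 90% interval, 4.2% to 32.8%, extends just below 5%.

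This rests on two assumptions: that 25% is meant as the alternative rate, which the rest of 13.2 supports, and that the stages run as planned with 13 and then 12 patients in the denominator.

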13.3 Stratification Factors

There are no planned stratification factors.

13.4 Interim Monitoring Plan

Enrollment will be paused at 13 patients to determine if there is sufficient efficacy to continue as outlined above.

13.5 Analysis of Primary Endpoints

The primary endpoint for this study is overall response rate in uveal melanoma by standard solid

tumor response criteria. The proportion of patients with best response of CR or PR will be presented with a 90% confidence interval estimated using the method of Atkinson and Brown, which allows for the two stage design.

13.6 Analysis of Secondary Endpoints

Secondary endpoints for this study include the rate of disease control, time to tumor progression, duration of response, safety of BVD-523, overall survival and correlative studies looking at drug effect and association of response with GNAQ and GNA11 mutation.

Disease control rate. The proportion of patients with best response of CR, PR, or SD lasting at least 24 weeks will be presented with a 90% exact binomial confidence interval. For a sample of size 25, the confidence interval will be no wider than 0.35.

Overall survival. Overall survival (OS) is the time interval between the start of treatment and death from any cause. OS will be censored at the date of the last follow-up visit for patients who become lost to follow-up.

Time to tumor progression. Time to tumor progression (TTP) is the time interval between the dates of the start of trial treatment and first documentation of progressive disease. In the absence of documented progressive disease, follow-up will be censored at date of last disease assessment.

Duration of response. Duration of response (DoR) is defined among patients with objective response (confirmed CR or PR as best overall response) as the interval between dates of first documentation of objective response and first documentation of progressive disease. In the absence of documented progressive disease, follow-up will be censored at date of last disease assessment.

The time-to-event endpoints will each be summarized using the method of Kaplan-Meier. Point estimates for each endpoint will be presented with 90% confidence intervals derived using log(-log(endpoint)) methodology.

Safety and Tolerability. All adverse events recorded during the trial will be summarized. The incidence of events that are new or worsening from the time of first dose of treatment will be summarized according to system organ class and/or preferred term, severity (based on CTCAE grade), type of adverse event, and relation to study treatment. Deaths reportable as SAEs and non-fatal serious adverse events will be listed by patient and tabulated by primary system organ class, and type of adverse event.

Association between GNAQ mutation and outcome. To explore the association between GNAQ mutation and clinical outcome, tumors will be classified according to whether or not there is GNAQ mutation and compared with therapeutic response. The relationship between GNAQ mutation and progression-free survival will be explored using the method of Kaplan-Meier. Time to disease progression will be calculated, stratified by GNAQ mutation status.

Association between changes in levels of GNAQ, GNA11 or ERK effectors and outcome. Changes

in GNAQ or GNA11 expression, or change in ERK targets, will be documented with immunohistochemistry of tumor. Biopsies and blood/serum samples will be collected pre-treatment and 12-16 days after first treatment. Pre-treatment levels will be considered as predictors of clinical efficacy; changes in expression between pre- and post-treatment samples will also be related with clinical outcome. Pre-treatment levels and percent changes will be summarized using descriptive statistics.

For the analysis of association between change in biomarkers levels and response, we anticipate that approximately 90% of patients will have tissue for analysis at pre-treatment and again at 12-16 days, resulting in a potential sample size of 23 patients with paired biopsies. For a response rate of 0.25, this would result in six patients with response and 17 non-responders. Comparisons of biomarker change measured on a continuous scale will be based on two-sided Wilcoxon rank-sum tests with a type-I error of 0.1. There will be at least 80% power to detect differences in biomarker change that are approximately 1.35 times the common standard deviation of the change.

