5.2.7 End of Treatment Visit

To be completed 20 to 30 days after the last dose of study drug.

- Physical examination
- Vitals (temperature, HR, BP and RR)
- Weight
- Performance status
- Record concomitant medications
- Laboratory Assessments

- Hematology
- Serum chemistry
- Serum lipase and amylase
- PT and aPTT
- Urinalysis
- Serum pregnancy test for WOCBP
- 12-lead ECG. If an ECG shows QTc prolongation (>470 milliseconds), the ECG must be repeated twice to obtain values in triplicate.
- Radiologic imaging studies: CT or MRI of chest, abdomen and pelvis followed by response evaluation to evaluate tumor status if the last scans were performed more than 4 weeks prior. MRI scan of the brain and additional imaging may be obtained as clinically indicated.
- Record AEs
- Eye Examination, will be performed by an ophthalmologist, or designated member of the clinical team, to check the participants vision and measure the pressure level in their eyes.

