5.6 Duration of Follow Up

Participant survival information will be collected, preferably via office visit or telephone contact, every 4 weeks (\pm 1 week) from the date of last dose of study drug until the participant's death or until the participant is lost to follow-up, or until study closure (approximately 6 months after the last participant terminates treatment). A participant will be determined to be lost to follow-up only after at least 3 attempts to contact him/her have been made over a 4-month period. At least two of these attempts to contact must be made through certified letters.

The following information will be collected:

- The participant's survival status, and if deceased, the date of death.
- The method by which the survival status was assessed and the date it was assessed.
- Any subsequent anti-cancer therapy received after discontinuation from study drug.

In addition, survival participants removed from study for unacceptable adverse events will be followed for resolution or stabilization of the adverse event.

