As response is the primary endpoint of this trial, participants with measurable and/or non-measurable disease will be assessed by RECIST criteria. For the purposes of this study, participants should be reevaluated every 8 weeks. In addition to a baseline scan, confirmatory scans should also be obtained no earlier than 4 weeks following initial documentation of an objective response.

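### Duration of response is defined twice: Section 11.1.5 counts death from any cause as an event, Section 13.6 censors it

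*Combined protocol and SAP*

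**What the plan says.** Section 13.6, the analysis section, defines DoR among confirmed responders as the interval between "response and first documentation of progressive disease. In the absence of documented progressive disease, follow-up will be censored at date of last disease assessment". Kaplan-Meier is the summary method, with 90% log(-log) intervals.

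Section 11.1.5 ends the duration of overall response at documented recurrence or progression, judged against the smallest measurements "since the treatment started, or death due to any cause. Participants without events reported are censored at the last disease evaluation". The definition of duration of complete response in the same section also ends at progression or death from any cause.

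No text says that one section overrides the other, or that two versions of DoR are intended.

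**The concern.** The two rules treat one kind of patient differently: a responder who dies with no progression on record. Under 11.1.5 that patient has an event on the date of death. Under 13.6 the patient is censored at the last disease assessment, as if future follow-up would have resembled that of the responders still at risk. For a patient who has died, that assumption is doubtful, so the censoring is likely to be informative.

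The same data can therefore give two DoR curves and two medians. If the choice is left until the data are in, it can be made knowing which answer looks better.

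**Working it through.** **1. Definitions side by side**

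| Responder's course | 11.1.5 | 13.6 |
|---|---|---|
| Progression documented | Event at progression | Event at progression |
| Alive, no progression | Censored at last assessment | Censored at last assessment |
| Dies, no progression documented | Event at death | Censored at last assessment |

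Only the third row differs. A misplaced closing bracket in the overall-response sentence of 11.1.5 puts the death clause inside the remark on reference measurements. The complete-response definition repeats the clause without that fault, so the intent is clear. Section 11.1.6 also separates an endpoint with death (progression-free survival) from one without (time to progression). The DoR censoring sentence in 13.6 is the one 13.6 uses for time to progression.

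**2. Can the third row occur?**

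Scans run every 8 weeks on treatment. The introduction to Section 11 says "confirmatory scans should also be obtained no earlier than 4 weeks following initial documentation of an objective response", so a responder who stops early may have little imaging after first response. The end-of-treatment scan (5.2.7) is needed only "if the last scans were performed more than 4 weeks prior". After that, Section 5.6 collects "The participant's survival status, and if deceased, the date of death" and "Any subsequent anti-cancer therapy received after discontinuation from study drug", with no scheduled imaging. For patients who stop because of symptomatic deterioration, 11.1.4.4 adds: "Every effort should be made to document the objective progression even after discontinuation of treatment". That reduces such cases but does not exclude them.

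**3. How many responders**

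The plan gives no figure for DoR. Its design figures (13.2) reproduce from the exact binomial with 13 then 12 patients: stopping probability at 5% is 0.8646 (stated 0.86), type I error 0.0755 (stated 8%), power 0.8668 (stated 87%).

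The continuation rule is: "If two or more responses are seen, an additional 12 patients will be enrolled into the second stage of the trial". With X1 ~ Bin(13, p), expected responders = 13p + P(X1 ≥ 2) × 12p. At p = 0.25 this is 3.25 + 0.8733 × 3 = 5.87.

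| True rate | Expected responders | P(at least 3) |
|---|---|---|
| 25% | 5.9 | 87% |
| 20% | 4.4 | 75% |
| 15% | 3.0 | 56% |
| 10% | 1.8 | 31% |
| 5% | 0.7 | 8% |

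**4. Effect of one such death**

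The layouts are assumptions, since the documents give no rate or timing. Times are weeks from first response. The median is the first time S(t) ≤ 0.5.

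*Short gap.* Six responders: five progress at 8, 16, 24, 32 and 40; one has a last scan at 8 and dies at 12.
- 11.1.5: S = 5/6 = 0.833 (week 8), × 4/5 = 0.667 (12), × 3/4 = 0.500 (16). Median 16.
- 13.6: S = 5/6 = 0.833 (8), one censored, × 3/4 = 0.625 (16), × 2/3 = 0.417 (24). Median 24.

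*Long gap.* Five responders: four progress at 8, 16, 24 and 32; one has a last scan at 4 and dies at 60.
- 11.1.5: S = 4/5 = 0.8 (8), × 3/4 = 0.6 (16), × 2/3 = 0.4 (24). Median 24.
- 13.6: one censored at 4, then S = 3/4 = 0.75 (8), × 2/3 = 0.50 (16). Median 16.

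Moving the death week in the long-gap layout, the 13.6 median stays at 16. The 11.1.5 median is 16 for death up to week 16, equals the death week from 17 to 24, and is 24 after that.

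**5. Direction**

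If nobody else progresses between the last scan and the death, the curves agree until the death, only 11.1.5 drops there, and later risk sets are identical. The 13.6 median is then equal or longer. With responses ending at 8-week steps and the death 4 weeks after its last scan, it is longer in 1 of 3, 2 of 4, 2 of 5, 3 of 6 and 3 of 7 positions for 3 to 7 responders, and otherwise equal.

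If others progress in the gap, 13.6 has already removed the patient from the risk set, and its median can be shorter (the long-gap case) or longer. With six responders, last scan at 4 and death at 12, it is 24 against 16.

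**The case against.** The strongest reply concerns weight. DoR appears in neither list of objectives (1.3 and 13.1); it enters only through the endpoint list in 13.6, and no test, precision target or decision rests on it. The planned 90% intervals are wide: in the short-gap layout the interval for the median is 8 to 32 weeks under 11.1.5, and under 13.6 it runs from 8 to no less than 40, so an 8-week shift lies inside both. The effect also needs a confirmed responder who dies without documented progression, which may not happen. The long-gap layout is unusual: the patient must stop early for a reason other than progression, have no later imaging and survive 56 weeks after the last scan. Finally, 13.6 may be deliberate, and counting a late death as the end of response credits unscanned time as response.

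Most of this stands as a limit on importance. It does not remove the conflict: a named secondary endpoint has two definitions, and wide intervals do not make it acceptable to choose between them after the data are seen. The short-gap case needs nothing unusual. The unscanned-time point is a real cost of the 11.1.5 rule and calls for disclosure. It is also fair that neither section says how DoR treats therapy started after study drug.

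**Conclusion.** The concern holds. Sections 11.1.5 and 13.6 give different event definitions for DoR, and nothing in the documents resolves them. One responder who dies without documented progression can leave the median unchanged or move it by 8 weeks in either direction in the layouts examined, which rest on assumed timings and 3 to 7 responders. If there is no such death, the results are identical. If the true response rate is 5%, the trial stops with 0 or 1 responder with probability 0.86, and the point has little weight. The primary response rate and the two-stage rule are unaffected. It should be fixed before analysis.

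**What to change.** In 13.6, define the DoR event as documented progression or death from any cause, as 11.1.5 does, and censor only responders alive without documented progression, at the last disease assessment. Correct the bracket in 11.1.5. Report how many responders died without documented progression and, for each, the time from last scan to death. State how DoR treats therapy started after study drug.

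The cost is wording only. Death dates and subsequent therapy are already collected under 5.6, and no visit, scan or patient is added. The reported DoR may become shorter or longer, or stay the same. Where death comes long after the last scan, unscanned time counts as response, which is why the scan-to-death interval belongs beside the estimate.

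A minor wording point for the same edit: 13.6 censors overall survival at the last follow-up visit, and 11.1.6 at the date last known alive. Because 5.6 accepts telephone contact, the practical difference is small, but the two should match.
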